8. STUDY ASSESSMENTS AND PROCEDURES

8.1. Administrative Procedures

The investigator (or an appropriate delegate at the investigator site) must obtain a signed and dated ICD before performing any study-specific procedures.

Study procedures and their timing are summarized in the SoA. Protocol waivers or exemptions are not allowed.

Adherence to the study design requirements, including those specified in the SoA, is essential and required for study conduct.

All screening evaluations must be completed and reviewed to confirm that potential participants meet all eligibility criteria. The investigator will maintain a screening log to record details of all participants screened and to confirm eligibility or record reasons for screening failure, as applicable.

Chest imaging conducted as part of the participant's routine clinical management (and obtained (within 12 weeks of Day 1) before signing of the ICD may be utilized for screening or baseline purposes provided the procedures met the protocol-specified criteria and were performed within the time frame defined in the SoA.

Every effort should be made to ensure that protocol-required tests and procedures are completed as described. However, it is anticipated that from time to time there may be circumstances outside the control of the investigator that make it unfeasible to perform the test. In these cases, the investigator must take all steps necessary to ensure the safety and well-being of the participant. When a protocol-required test cannot be performed, the investigator will document the reason for the missed test and any corrective and preventive actions that they have taken to ensure that required processes are adhered to as soon as possible. The study team must be informed of these incidents in a timely manner.

Laboratory results that have been collected for the purposes of this study and could unblind the study will not be reported to investigative sites or other blinded personnel.

For samples being collected and shipped, detailed collection, processing, storage, and shipment instructions and contact information will be provided to the investigator site prior to initiation of the study.

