8.3.6. Clinical Safety Laboratory Assessments

See Appendix 2 for the list of clinical safety laboratory tests to be performed and the SoA for the timing and frequency. All protocol-required laboratory assessments, as defined in Appendix 2, must be conducted in accordance with the laboratory manual and the SoA. Unscheduled clinical laboratory measurements may be obtained at any time during the study to assess any perceived safety issues.

The investigator must review the laboratory report, document this review, and record any clinically significant changes occurring during the study in the AE section of the CRF. Clinically significant abnormal laboratory test findings are those that are not associated with the underlying disease, unless judged by the investigator to be more severe than expected for the participant's condition.

All laboratory tests with values considered clinically significant and abnormal during participation in the study or within 28 days after the last dose of study intervention should be repeated until the values return to normal or baseline or are no longer considered clinically significant by the investigator or study medical monitor.

If such values do not return to normal/baseline within a period of time judged reasonable by the investigator, the etiology should be identified and the sponsor notified.

See Section 10.5 for suggested actions and follow-up assessments in the event of potential DILI.

See Section 10.6 for instructions for laboratory testing to monitor kidney function and reporting laboratory test abnormalities.

For laboratory collection volumes, see the laboratory manual.

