10.2. Appendix 2: Clinical Laboratory Tests

The following safety laboratory tests will be performed at times defined in the SoA section of this protocol. Additional laboratory results may be reported on these samples as a result of the method of analysis or the type of analyzer used by the clinical laboratory, or as derived from calculated values. These additional tests would not require additional collection of blood. Unscheduled clinical laboratory measurements may be obtained at any time during the study to assess any perceived safety issues.

Table 7. Protocol-Required Safety Laboratory Assessments

Homotology	Hematology Chemistry Urinalysis Other Reflex Tests			
Hematology CBC with	Chemistry Urea and	Urinalysis		Reflex Tests
differentials ^a	creatinine,	Local dipstick:	At screening: • FSH ^d	Required Tests:
Hemoglobin	Cystatin C (at	Protein (qual)		For suspected DILI: AST/ALT
Hematocrit	baseline)	Blood (qual)	Pregnancy test	T bili, direct and indirect
RBC count	Sodium	Nitrites	(β-hCG) ^e	bili
	Potassium		• TBf	
Platelet count		Leukocyte	 HBsAg (if 	Total bile acids, GGT
WBC count: Full	AST, ALT	esterase	equivocal, reflex	Total protein, albumin
differential	Total bilirubin Alkaline	T 1	to HBV DNA	CK DT. IND
including %		Laboratory:	quantification)	PT, INR
Total neutrophils	phosphatase	Microscopy	• HBcAbg	Acetaminophen/paracetamol
(Abs and %)	Albumin	and culture ^c	• HBsAbg	or
Eosinophils (Abs	Total protein		HCVAb (if	protein adduct levels
and %)	GFR ^b		positive, reflex	Hepatitis serology (even if
Monocytes (Abs			to HCV RNA	screening negative)
and %)			quantification)	E 1 DIGUDIU
Basophils (Abs			 HIV serology 	For suspected DICI/DIKI:
and %)				Creatinine (Scr)
Lymphocytes				Cystatin C (Scys)
(Abs and %)				eGFR (Scr only and
TDMI D 10				combined Scr+Scys)
TBNK Panela				Spot (dipstick) UACR
Total T-Cells				
(CD3+), B cells				
(CD3-CD19+),				
NK cells (CD3-				
CD16+CD56+),				
CD4+ Tcells				
(CD3+CD4+) and				
CD8+ Tcells				
(CD3+CD8+)				
count (Abs and %)				
Coagulation Panel				
aPTT				
INR				
PT				

a. Site staff, including Investigators, will be blinded to the WBC count, WBC differential (percentage and absolute number), and TBNK panel cell counts; results will be assessed by an unblinded Independent medical monitor who will notify Investigators when participants experience events of Grade 4 lymphopenia (ALC < 0.2 × 109 cells/L) and will direct Investigators on specific actions to take. Refer to Section 10.10.1

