10.10. Appendix 10: Safety Monitoring Guidance

This study will utilize 2 medical monitors:

The unblinded independent medical monitor

- is a clinician independent from and not a member of the study team
- monitors unblinded WBCs and TBNK values while remaining blinded to study treatment
- will notify investigators when participant has Grade 4 lymphopenia (ALC < 0.2 × 109 cells/L) and will direct investigators on specific actions to take (outlined in Protocol Section 10.10.1)
- will notify investigators when there is at least 1 measurement of ANC $< 1.0 \times 10^9$ cells/L or WBC count $> 20 \times 10^9$ cells/L (outlined in Protocol Section 10.10.1)

The blinded study medical monitor:

- is a Pfizer clinician and a blinded member of the C5041005 study team
- should be contacted for questions on the protocol, eligibility (including roll-over to the OLE) and continuation criteria based on EASI-50
- Should be contacted if participant does not meet discharge criteria after 4 hours of cardiac monitoring (outlined in Protocol Section 10.10.3)
- Should be contacted when referenced as the "study medical monitor" in the protocol, in cases of overdose, protocol predefined study intervention interruption and re initiation, suspected cases of PML (outlined in Protocol Section 10.11), and for all other safety concerns.

Temporary Interruption to Dosing

Dose interruptions are defined as the following consecutive days of missed study treatment:

- \geq 2 consecutive days within the first week of treatment and Week 16 of Part 1, or
- ≥7 consecutive days after the first week of treatment (excluding Week 16 of Part 1 where missing 2 doses applies)

If the Investigator deems it necessary to withhold study treatment due to an adverse event, temporary withholding is permitted for up to 6 days (after the first week of treatment) without obtaining prior approval from the study medical monitor. Planned dose interruptions during the first week of treatment requires consultation with the study medical monitor. If study treatment interruption ≥ 7 days is required for a medical reason at any time in the study, the Investigator must contact the study medical monitor for further instruction as soon as this is anticipated.

[figure not shown]

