10.10.1. Monitoring Of Lymphocyte, Neutrophil, and White Blood Cell Counts

Etrasimod prevents lymphocyte egress from lymphoid tissues, resulting in a reduction in peripheral lymphocyte count and lymphocyte availability for recruitment to sites of inflammation. Site staff, including Investigators, will be blinded to the WBC count, WBC differential (percentage and absolute number) and TBNK panel cell counts. WBC count, WBC differential, and TBNK panel results will be assessed by the unblinded independent medical monitor who is not involved in any other aspects of study conduct or data analysis and who is blinded to study treatment. The unblinded independent medical monitor will notify Investigators when participants experience events of Grade 4 lymphopenia (ALC $< 0.2 \times 10^9 \ \text{cells/L}$) and will direct Investigators on specific actions to take as described in Figure 1. Participants must permanently discontinue study treatment in the event of sustained Grade 4 lymphopenia, defined as a second confirmed Grade 4 measurement with treatment rechallenge after study treatment interruption.

Figure 1: Management of Grade 4 Lymphopenia Events

*If repeat assessment does not confirm Grade 4 lymphopenia, continue study treatment. If study intervention has been interrupted ≥ 2 consecutive days during Week 1 or Week 16 of Part 1 or ≥ 7 consecutive days after Week 1 (excluding Week 16 of part 1 where 2 doses applies), First Dose Cardiac Monitoring must be conducted when study intervention is re-initiated (see Section 10.10.3).

In addition, the unblinded independent medical monitor will notify Investigators when there is at least 1 measurement of ANC $< 1.0 \times 10^9$ cells/L or WBC count $> 20 \times 10^9$ cells/L. Blinded values may be released to treating physicians and Investigators as deemed medically necessary to monitor the risk of infection and/or aid in diagnostic workup as clinically indicated, and/or as a tool to assess the effectiveness of therapeutic interventions for an infection. Investigators will repeat CBC with differentials weekly until ANC $> 1.0 \times 10^9$ cells/L or the increased WBC count trends downward (on 2 separate days), respectively.

Participants with an ongoing AE of decreased lymphocyte count or infection at the 4-Week Follow Up Visit should return for CBC with differential according to local standard of care (captured as subsequent Follow-Up Visit or unscheduled visit).

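### Blood counts after the 4-week follow-up visit hinge on a lymphocyte AE that blinded investigators have no routine way to identify below Grade 4

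*Protocol*

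**What the plan says.** Protocol Section 10.10.1 sets the rule for counts after the second safety follow-up visit (SFU 2, 4 weeks after the last dose): "Participants with an ongoing AE of decreased lymphocyte count or infection at the 4-Week Follow Up Visit should return for CBC with differential". The schedule of those counts is left to local standard of care. There are two triggers, an ongoing AE of decreased lymphocyte count or an ongoing infection, and neither carries a grade limit.

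The same section states: "Site staff, including Investigators, will be blinded to the WBC count, WBC differential (percentage and absolute number) and TBNK panel cell counts". Table 7 footnote a (Section 10.2) repeats this almost word for word. Neither place exempts any part of the study. Section 8.1 adds: "Laboratory results that have been collected for the purposes of this study and could unblind the study will not be reported to investigative sites", and extends this to other blinded personnel.

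The independent medical monitor sees the counts. For lymphocytes, Section 10.10 gives that monitor one routine duty towards sites: "will notify investigators when participant has Grade 4 lymphopenia (ALC < 0.2 × 109 cells/L"). The other stated notices concern ANC below 1.0 and WBC above 20 × 10^9/L.

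Section 8.3.6 has a general rule that clinically significant abnormal results "should be repeated until the values return to normal or baseline or are no longer considered clinically significant by the investigator or study medical monitor". Section 10.10 says of the study medical monitor that this person "is a Pfizer clinician and a blinded member of the C5041005 study team".

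**The concern.** The post-SFU 2 rule asks the investigator to act on an AE whose evidence is a laboratory value withheld from that investigator. Below Grade 4, no passage gives a routine step by which the investigator learns that the count is low, or that it is still low at SFU 2. The back-up rule in Section 8.3.6 has the same weakness, because both people it names are blinded.

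At stake is whether an existing safety rule can work. Section 10.10.2 links low lymphocyte counts on other S1P modulators to serious and atypical infections and asks for vigilance after treatment stops. A participant whose count is slow to recover is the one the rule is meant to keep in view. Active AE collection is required only for a minimum of 4 weeks after the last dose (Section 8.4.1), so SFU 2 is the natural point to identify such a participant.

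**Working it through.** No sample-size or power figure is involved. The check sets the passages side by side.

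1. **What the trigger needs.** A recorded, ongoing AE of decreased lymphocyte count (10.10.1). Recording it requires knowledge of the count.
2. **What the recorder sees.** Not the WBC count, differential or TBNK panel (8.1, Table 7 footnote a, 10.10.1).
3. **What the recorder is routinely told about lymphocytes.** Only ALC below 0.2 × 10^9/L (10.10, 10.10.1). Figure 1 is not shown in the text available, but its title limits it to Grade 4 events.
4. **Band without a routine notice.** Entry requires ALC of at least 1.0 × 10^9/L (exclusion criterion 10). Counts from 0.2 to below 1.0 × 10^9/L are therefore under the entry floor but produce no routine lymphocyte notice. The entry floor serves only as a reference mark from the protocol, not as a definition of clinical significance.
5. **Timing.** Section 2.3.1 reports reversal to normal within 2 to 4 weeks. SFU 2 is at 4 weeks ± 3 days, that is 28 − 3 = 25 to 28 + 3 = 31 days after the last dose, which is the outer end of that period. Hematology is scheduled at both follow-up visits and TBNK at SFU 2 (Sections 1.3.2 and 1.3.3). The relevant count is therefore taken and reviewed by the independent monitor, but no passage tells that monitor to report a low value above the Grade 4 limit.
6. **Non-routine routes below Grade 4.**
   - Release: "Blinded values may be released to treating physicians and Investigators as deemed medically necessary to monitor the risk of infection" (10.10.1). It has no grade limit, but it is discretionary and tied to infection risk, work-up or treatment.
   - Contact: Section 8.3.6.1 tells sites with a question or safety concern about this testing to contact the independent monitor. The site must first have a reason to ask.
   - Local laboratory: Section 8.3.6.1 allows it in Part 1 OLE and Part 2 when the participant cannot reach the site, and site staff then receive and review the results. Sections 8.1.2 and 8.1.3 also allow local blood work in those parts, but the remote visits they list include SFU 1 and not SFU 2.
   - Infection: a separate trigger, which fires only once an infection is present.
7. **Where the gap is clearest.** For participants who do not enter the OLE, Section 8.3.6.1 bars local WBC and TBNK testing in the double-blind period and its follow-up unless clinically urgent. About 60/2 = 30 participants are randomized to etrasimod. The affected group is those of the 30 who do not continue, multiplied by the share still low at SFU 2. Neither quantity is given, so the possible range is 0 to 30. If 5% to 10% of all 30 were affected (an assumption), the number would be 0.05 × 30 = 1.5 to 0.10 × 30 = 3.
8. **A second inconsistency.** The blinding statements cover all parts, yet the local-laboratory provisions let site staff see counts in Part 1 OLE and Part 2. Part 2 is open-label with a single arm, and Section 8.1 withholds only results that could unblind. The documents do not settle whether the count blinding applies in those parts.

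**The case against.** The strongest reply is that several routes exist and the quantity at stake is small. The release clause has no grade limit, sites have a line to the independent monitor, local results are visible in Part 1 OLE and Part 2, and infection triggers follow-up by itself. Lymphocyte reduction is an expected pharmacodynamic effect with quick reported reversal, and a count below baseline is not automatically an AE. The current amendment also moved this rule away from a fixed laboratory cut-off on purpose. All of this stands. It shows that a low count can come to light, but not that any routine step brings it to light.

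Three stronger readings are tempting and are not supported:

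- A reader might infer that investigators cannot record a lymphocyte AE below Grade 4 at all. The routes above show otherwise.
- A reader might infer that most unresolved lymphopenia goes unfollowed, or apply an assumed 5% to 10% to 60 + 340 = 400 planned participants and arrive at 20 to 40 people. The documents give no distribution of counts at SFU 2, the reported reversal takes 2 to 4 weeks, and local results may be visible in the OLE and Part 2.
- A reader might infer that slow reversal would go undescribed. SAP Section 6.5.2 summarizes hematology, including TBNK, by visit, and SAP Appendix 2.1 reports follow-up safety data at nominal visits (Weeks 70 and 72 in Part 1, 54 and 56 in Part 2). Non-recovery at SFU 2 is measured and reported. What may be missing is the course after SFU 2.

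**Conclusion.** The concern holds as an internal inconsistency in the protocol. Below Grade 4, the lymphocyte half of the Section 10.10.1 trigger depends on an AE that a blinded investigator has no routine way to identify, and Section 8.3.6 does not close the gap. It is clearest for Part 1 participants who leave after the double-blind period. In Part 1 OLE and Part 2 its extent depends on whether the count blinding applies there, which the documents leave open.

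The number affected cannot be derived and may be small. The conclusion rests on reading the blinding statements as written and on the absence, in the text available, of any other notification duty for sub-Grade 4 counts. The efficacy analyses are not touched. The point is worth correcting because an existing safety rule should be able to operate, not because a large number has been shown.

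**What to change.** Reconcile Sections 10.10.1 and 8.3.6 with the blinding in Section 8.1, Table 7 footnote a and Section 10.10.1, and with the local-laboratory provisions in Sections 8.1.2, 8.1.3 and 8.3.6.1. Two statements are needed:

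- Follow-up after SFU 2 is prompted by someone who can see the SFU 2 counts, namely the existing independent medical monitor, and does not depend on an AE that the blinded investigator has no routine way to identify.
- Whether the blinding to WBC, differential and TBNK applies in Part 1 OLE and Part 2.

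No level, threshold or clinical rule is proposed here; those are for the sponsor. The reference to local standard of care for the return counts can stay.

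The cost is protocol wording. It needs no new staff or scheduled test, since the counts are already drawn and reviewed and Section 10.10.1 already provides for an unscheduled visit. The downside is some extra notifications and unscheduled CBCs after treatment ends. A notice about a participant who left after the double-blind period could also hint at the assigned arm. By then, however, the Week 16 response is either recorded or already set to non-response under the primary estimand.

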10.10.2. Serious Infections Monitoring

Low lymphocyte counts observed with the use of other S1P receptor modulators in patients with multiple sclerosis have been associated with serious and atypical infections. ^{4,5,46} Investigators should remain vigilant in monitoring for signs and symptoms of serious and atypical infections during the study and after discontinuation of study treatment. Serious infection monitoring (refer to definition for Serious Adverse Events in Section 10.3.2) requires a temporary interruption of study intervention. Study intervention cannot be restarted until the serious infection has resolved per investigator judgement (investigator may discuss restarting study intervention with the medical monitor, if needed). If the participant cannot be restarted on study intervention, then the participant must be permanently discontinued.

Participants will be queried for signs and symptoms of PML. If a participant exhibits signs and symptoms suspicious for PML, study treatment must be interrupted and cannot be restarted until diagnostic evaluation is completed and PML has been excluded. The study medical monitor should be informed of any suspected cases of PML. Refer to Section 10.11 for signs and symptoms of PML and a PML case evaluation algorithm. In the evaluation and management of treatment emergent infections, the Investigator may consult with infectious disease or relevant experts, as needed.

All radiologic images (eg, magnetic resonance imaging, computer tomography, X rays) and diagnostic laboratory test results performed by local laboratories/facilities should be retained as source documents by study sites and made available upon request by the Sponsor for central adjudication as needed. All infections that develop during the study will be reported as AEs on the AE eCRF page.

10.10.3. First-Dose Cardiac Monitoring

Cardiac monitoring following treatment initiation applies to the first dose administered in the Treatment Period (Day 1). Day 1 predose (ie, Baseline) vital signs (resting HR, BP, body temperature, and respiratory rate) will be used as the baseline measurements. The lowest predose HR measurement (by vital signs) will be used for comparison to the postdose measurement. It should be noted that in this section heart rate refers to pulse rate. Pulse rate will be collected as part of vital signs and heart rate will be collected as part of the ECG.

Cardiac monitoring is required at the Day 1 (first blinded dose) of Part 1 and Part 2 and Week 16 (first open label etrasimod dose) of Part 1 and will also be necessary to reinitiate study treatment if consecutive days of study treatment are missed as described in Section 7.1.7. These visits for cardiac monitoring should be conducted in the morning and not on a Friday or the day before a site-observed holiday. In the following sections describing first-dose cardiac monitoring, Day 1 refers to the first day of treatment in the Treatment Period, but the same procedures will also be used at the Week 16 visit in Part 1 (first open label dose) and the first day of treatment re-initiation following the defined periods of treatment interruption noted above. Day 2 refers to the subsequent dosing day.

10.10.3.1. Cardiac Monitoring Schedule After First Dose

After the first dose of study treatment on Day 1 of Part 1 and Part 2, participants will be observed up to 8 hours. Cardiac monitoring on the first 4 hours (0H, 1H, 2H, 3H and 4H) is required for all participants. The second 4 hours (5H, 6H, 7H, and 8H) are not required and will only be performed for participants who do not meet discharge criteria at hour 4 of cardiac monitoring. The in-clinic cardiac monitoring on Day 1 will include assessments at the timepoints specified in Table 8. These criteria will also be used at the Part 1 Week 16 visit, the first day of treatment re-initiation following the defined periods of treatment interruption, and for Day 1 Part 2 of the study.

Participants who do not meet discharge criteria at 4 hours postdose on Day 1 will require extended cardiac monitoring on Day 1 (Table 8) and on Day 2, as described in Section 10.10.3.1.2.

For participants who experience a cardiovascular symptomatic event (eg, chest pain, dizziness, palpitations, lightheadedness, shortness of breath, and/or syncope) at any time during the first 4-hours postdose (ie, on Day 1), the Investigator should determine whether or not this event is associated with a HR reduction or clinically relevant change in 12-lead ECG. Participants who experience a symptomatic event associated with HR reduction or clinically relevant 12-lead ECG should be discontinued from study treatment if they meet the criteria described in Section 10.10.3.2. Participants who experience a symptomatic event that is not associated with HR reduction or clinically relevant 12-lead ECG may be discharged on Day 1 at Hour 4 postdose (at the Investigator's discretion and provided they meet the discharge criteria (Section 10.10.3.1.1), but must return to the clinic on Day 2 for extended cardiac monitoring as described in Section 10.10.3.2.

Table 8. Procedures to be Performed During the First-Dose Cardiac Monitoring Period

Procedure	Predose	Hours 1, 2, and 3 Postdose ^a	Hour 4 Postdose ^a	Day 1 Extended Cardiac Monitoring ^b
Blood pressure and HR derived from vital signs (seated position)	Xe	X°	X°	X ^c
12-lead ECG (supine position) ^d	X	_	X	X
Assess discharge criteria	_	_	X	X

- Measurements may be taken within \pm 15 minutes of the scheduled time. Record time of assessment.
- b Only for participants not meeting discharge criteria (Section 10.10.3.1.1) at Hour 4. Assessments should be repeated hourly (\pm 15 minutes of the scheduled time) until the participant meets the discharge criteria; the blinded study medical monitor should be contacted if the participant does not meet the discharge criteria after 4 hours of extended cardiac monitoring on Day 1. Record time of assessment.
- c If the participant has a vital sign HR of < 50 bpm or if cardiovascular symptoms develop (eg, chest pain, dizziness, palpitations, and/or syncope associated with reduction of HR), conduct 12-lead ECGs as clinically indicated. Include body temperature and respiratory rate.
- d Additional 12-lead ECGs may be conducted as clinically indicated.
- e Include body temperature and respiratory rate.

